2.4 Study Objectives

The aim of this trial is to verify the safety and performance of the ARGOS-IO system in patients with Primary Open Angle Glaucoma (POAG) and indicated cataract surgery. The measurements of intraocular pressure through the pressure sensor shall be compared with Goldmann Applanation Tonometry (GAT), which is generally accepted as the clinical gold standard. The ARGOS-IO pressure sensor will be implanted during cataract surgery and is to remain permanently in the eye.

2.4.1 Primary Objectives

The primary objectives of this clinical investigation are

- **Safety:** To evaluate the safety and tolerability of the ARGOS-IO pressure sensor in the first 3 months following implantation.
- **Performance:** To evaluate the performance of the ARGOS-IO system compared to GAT from day 30 through day 180.

2.4.2 Secondary Objectives

The secondary objectives of this clinical investigation are

- **Safety:** To evaluate the safety and tolerability of ARGOS-IO pressure sensor implantation between 3 and 12 months.
- **Performance:** To evaluate the performance of the ARGOS-IO system compared to GAT up to 12 months after implantation.

2.5 Study Hypothesis

The specific hypothesis to be tested in this single arm two-stage design study is that the SADE rate is lower than 25%. It is expected that the observed SADE rate will be at most 6%. More precisely, let p be the true proportion of subjects with no SADEs, p_0 the proportion of subjects no SADE to be rejected and p_1 the expected proportion of patients overall without SADE. Then, the null hypothesis H_0 and the alternative hypothesis H_1 are:

$$H_0 = p \leq p_0 = 0.25 \quad \text{vs.} \quad H_1 = p > p_1 = 0.25.$$

If at most 2 SADE's occur in the 22 patients enrolled, a SADE rate lower than 25% can be concluded. This will be illustrated by the 95% confidence interval for the SADE rate which will be calculated using the method proposed by Koyama (Koyama & Chen, 2008). If the obtained

confidence interval does not include any value lower than 0.94, it can be concluded that the SADE rate is at most 6%.

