Page 87, 9.2 Sample Size Calculation:

RevC

The sample size calculation was based on the study's purpose of establishing safety.

To minimize the required sample size and consequently the number of patients exposed to risk while at the same time maximizing the chances of detecting safety events, a two-stage design based on the rate of non-events was chosen (Simon, 1989). The event of interest was defined as a serious device-related adverse events (SADEs). Based on a probability of non-events of $p_0=0.75$ for the first stage and an overall acceptable probability of $p_1=0.94$, a sample size of at least 11 evaluable patients in the first stage and additional 11 patients in the second stage are required. This maintains a type 1 error

probability of 5% and the power of 80% based on minimizing the maximal sample size and results in an expected sample size of 13.2 patients.

Ammended

The primary aim of this study is to show “safety”, which will be evaluated based on the percentage of subjects who experience an SADE (= “non-safety), as defined in the primary endpoints.

The study will be declared a success if the final non-safety event rate is less than 6% (type II error rate of 0.20) The calculation is based on a design optimizing the minimum expected sample size with parameters $\alpha=0.05$, $\beta=0.20$, $p_0=0.75$, $p_1=0.94$. According to Table 7, those parameters will be fulfilled if 2 or less SADE will occur in a sample of 22 patients.

Part 2: Interim Analysis

Page 16, Table: Synopsis, Row: Data Analysis and Statistics, Item: Interim Analysis:

RevC

An interim analysis to assess SADE will be performed, when the first 11 patients have completed the 3 month follow-up visit.

Ammended

An interim analysis to assess Safety and Performance will be performed, when the all patients have completed the 6 month follow-up visit or if an SADE occurs.

Page 87, 9.6 Interim Analysis:

RevC

One interim analysis is planned for this study. It will take place when all patients in the first stage have completed the first 3 months of the follow-up period and will determine whether or not to continue the study to the second stage based on the number of patients experiencing an SADE..

Ammended

An interim analysis is planned for this study. It will take place when all patients have completed 6 month follow-up period, or each time an SADE occurs, prior to the regular DSMB meeting

Part 3: Implant size selection

Page 74, 8.4.4.13 ARGOS-IO implant size assessment:

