2.1 Study Design

The trial will be conducted as an open, prospective, multicenter single-arm clinical trial following the principle of the two-stage design described by Simon (Simon, 1989) in patients with Primary Open Angles Glaucoma (POAG) and indicated cataract surgery. The purpose is to evaluate the safety of the ARGOS-IO system and to compare its performance to the Goldmann Applanation Tonometry (GAT).

All 22 patients will be enrolled consecutively, until a serious adverse device effect (SADE) occurs. In that case, the DSMB will be called, and decides whether the enrollment can be continued or not.

An interim analysis will be performed after half of the study population (11-14 subjects) is enrolled with a minimum follow-up of 1 month. Another interim analysis to assess Safety and Performance will be performed, when all patients have completed the 3 month follow-up visit, the 6 month follow-up visit and every time an SADE occurs.

In order to take the two-stage design described by Simon into account, the trial will be terminated, if more than 1 patient out of the first 11 patients enrolled experiences SADEs during the first 3 months of the post-surgical follow-up period.

A conclusion for safety will be made at the 5% significance level, if two or fewer of the total 22 patients experience an SADE. A corresponding 95% confidence interval for the SADE rate will be calculated according to the procedure of Koyoma (2008).

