2.9 Sample Size Calculation

The primary aim of this study is to show “safety”, which will be evaluated based on the percentage of subjects who experience an SADE (= “non-safety), as defined in the primary endpoints.. To minimize the required sample size and consequently the number of patients exposed to risk while at the same time maximizing the chances of detecting safety events, the sample size calculation follows the principle of a two-stage design as proposed by Simon (Simon, 1989). The event of interest was defined as patients with at least one serious device related adverse event (SADE) in the 3 month period immediately following implantation. Based on a probability of non-events of $p_0=0.75$ for the first stage and an overall acceptable probability of $p_1=0.94$, a sample size of at least 11 evaluable patients in the first stage and additional 11 patients in the second stage are required. This maintains a type 1 error probability of 5% and the power of 80% based on minimizing the maximal sample size. Table 2 summarizes the consequences of the sample size calculation on the study design.

Table 2: Two-stage study design

	First Stage	Overall
SADE-free Patients		
Proportion	$p_0 = 0.75$	$p_1 = 0.94$
Minimum number required	10	20
Patients with SADE		
Proportion	$1 - p_0 = 0.25$	$1 - p_1 = 0.06$
Maximum number allowed	1	2
Total Number of Patients	11	22

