2.10 Planned Interim Analysis

All 22 patients will be enrolled consecutively, until a serious adverse device effect (SADE) occurs. In that case, the DSMB will be called, and decides whether the enrollment can be continued or not.

An interim analysis will be performed after half of the study population (11-14 subjects) is enrolled with a minimum follow-up of 1 month (Visit 5). Another interim analysis to assess Safety and Performance will be performed, when all patients have completed the 3 month follow-up visit, the 6 month follow-up visit and every time an SADE occurs.

In order to take the principle of the two-stage design described by Simon into account, the trial will be terminated for futility if more than 1 patient out of the first 11 patients enrolled experience at least one SADE during the first 3 months of the post-surgical follow-up period.

The study will also be stopped if the DSMB otherwise determines that severe safety risks to the patients exist.

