7.2 Evaluation of Primary Safety Variables

Incidence of SADEs in the 3 month period immediately following implantation will be assessed. The decision on safety follows the rule of Simon's optimal two-stage design (parameters: $\alpha=0.05$, $\beta=0.20$, $p_0 = 0.75$, $p_1 = 0.94$). A corresponding 95% confidence interval will be given for the portion of SADEs within the safety population. The confidence interval for the SADE rate will be calculated using the method proposed by Koyama (Koyama & Chen, 2008). These calculations will be based on the number of patients experiencing a SADE based on the safety population. If the obtained confidence interval does not include any value lower than 0.94, it can be concluded that the SADE rate is at most 6%.

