8.1 Interim Analysis

All 22 patients will be enrolled consecutively, until a serious adverse device effect (SADE) occurs. In that case, the DSMB will be called, and decides whether the enrollment can be continued or not.

An interim analysis will be performed after half of the study population (11-14 subjects) is enrolled with a minimum follow-up of 1 month. Another interim analysis to assess Safety and Performance will be performed, when all patients have completed the 3 month follow-up visit, the 6 month follow-up visit and every time an SADE occurs.

In order to take the principle of the two-stage design described by Simon into account, the trial will be terminated if more than 1 patient out of the first 11 patients enrolled experience at least one SADE during the first 3 months of the post-surgical follow-up period.

For the interim analyses, the report will comprise the following tables and listings specified in the DSMB charter from 3rd June 2014:

- Information on patient screening – number of screening failures
- Patient recruitment by month and by institution
- Eligibility violations
- Summary tables:
 - Baseline characteristics including
 - Date of informed consent signatures
 - Demographics (Age, Gender, Race)
 - Weight, Height
 - Anterior and posterior segment examination results and abnormalities
 - GAT measurement
 - Number of subjects with Adverse events by System Organ Class and Preferred terms
 - Serious adverse events
 - Adverse events
 - Device-related adverse events
 - Medical history (Year of Glaucoma diagnosis, Type of Glaucoma, Study Eye, Previous/concomitant illnesses, conditions and procedures)
 - Concomitant medications
 - Anterior and posterior examination results and abnormalities (follow-up visits)
 - Surgery documentation including
 - Complications

- Incision location
- Iridectomy
- IOL Implantation and location of the IOL haptics
- ARGOS-IO pressure sensor implantation and location of ASIC
- In situ position of IOL and ARGOS-IO implant at all relevant follow-up visits
- GAT measurements (V01, V02, V03, V04)
- GAT and ARGOS-IO serial measurements (V05, V06, V07)
- Protocol deviations
- Device Deficiencies, if any
- Unscheduled Visits, if any
- Premature termination of patients including date and reason
- Pregnancy reports, if any

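### SAP 2.5 concludes a SADE rate below 25% from at most 2 of 22 without repeating the stage-1 limit; taken alone that rule has a type I error of 6.06%, whereas the two-stage rule named in SAP 7.2 has 4.97%

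*SAP*

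**What the plan says.** The SAP states the final decision on the primary safety endpoint in two ways.

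**Total only.** SAP 2.5 says "If at most 2 SADE's occur in the 22 patients enrolled, a SADE rate lower than 25% can be concluded". SAP 2.1 says "A conclusion for safety will be made at the 5% significance level, if two or fewer of the total 22 patients experience an SADE". Neither sentence mentions the first 11 patients.

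**Two-stage.** SAP 7.2, which prescribes the primary safety analysis, says "The decision on safety follows the rule of Simon's optimal two-stage design". Table 2 in SAP 2.9 allows at most 1 SADE patient in the first 11 and at most 2 in 22. Of that design SAP 2.9 says "This maintains a type 1 error probability of 5% and the power of 80"%. SAP 5.2 also refers to the critical value of Simon's design for this endpoint, and requires it to be recalculated if implanted patients drop out.

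**Termination.** The stage-1 limit also appears as a stopping instruction. In SAP 2.1, in the paragraph just before the conclusion sentence, it reads "the trial will be terminated, if more than 1 patient out of the first 11 patients enrolled experiences SADEs". In SAP 2.10 it reads "the trial will be terminated for futility if more than 1 patient out of the first 11 patients enrolled experience at least one SADE", and in SAP 8.1 "the trial will be terminated if more than 1 patient out of the first 11 patients enrolled experience at least one SADE".

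**Protocol addendum.** The addendum to Rev C removes the stage-1 column from the design table. In its amended section 9.2 it keeps alpha at 0.05 and says "those parameters will be fulfilled if 2 or less SADE will occur in a sample of 22 patients". The SAP follows Rev. G, which is not among the documents.

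**The concern.** The 5% level belongs to the two-stage rule. If the final claim rests on the total alone, it admits one extra route to success that the two-stage rule excludes, and the type I error exceeds 5%.

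In a conventional Simon trial this would be harmless shorthand, because a trial that fails stage 1 never reaches 22 patients. Here that cannot be assumed. Enrolment was consecutive, with a halt and a DSMB decision on continuing when a SADE occurred. The half-way interim analysis needs only 1 month of follow-up, while the stage-1 limit counts SADEs over 3 months. SAP 8.2 reports 21 subjects past Visit 5 at the first interim analysis independent from the DSMB. Once the second 11 patients are implanted, an instruction to terminate no longer has an effect on enrolment, and SAP 2.5 does not say that the limit still decides the claim.

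At stake is the only statistical test in the trial (SAP 5.3). For the one outcome on which the rules disagree, SAP 2.5 supports a claim of safety and SAP 7.2 does not.

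**Working it through.** **Inputs.** 11 + 11 patients, at most 1 SADE patient in stage 1 and at most 2 overall, p0 = 0.75 and p1 = 0.94 SADE-free (SAP 2.9 and 7.2). The SADE rate q is therefore 0.25 at the null and 0.06 at the design value. X1 and X2 are the numbers of SADE patients in the first and second 11, taken as independent Bin(11, q). The 0.25 printed for the SADE-free proportion in the hypothesis line of SAP 2.5 is a separate slip and is not used.

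**1. The plan's own figures.** Two-stage rule: P(conclude safety) = P(X1=0)·P(X2≤2) + P(X1=1)·P(X2≤1).

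- q = 0.25: 0.04224 × 0.45520 + 0.15486 × 0.19710 = 0.01923 + 0.03052 = 0.0497.
- q = 0.06: 0.50630 × 0.97524 + 0.35549 × 0.86178 = 0.49376 + 0.30635 = 0.8001.
- Expected N at q = 0.25: 11 + 11 × P(X1≤1) = 11 + 11 × 0.19710 = 13.17. Protocol 9.2 states 13.2.

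The stated 5%, 80% and 13.2 are all reproduced, so this is the design that was sized. A full search at these parameters returns 11/22 with limits 1 and 2 as both the optimal and the minimax design.

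**2. The SAP 2.5 rule alone.** P(Bin(22, q) ≤ 2):

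- q = 0.25: 0.00178 + 0.01308 + 0.04578 = 0.0606.
- q = 0.06: 0.25634 + 0.35996 + 0.24125 = 0.8576.

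**3. Where the rules differ.** Totals of 0 or 1 pass both rules and totals of 3 or more fail both. With exactly 2, only the split of 2 then 0 is treated differently. Its probability is P(X1=2)·P(X2=0):

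- q = 0.25: 0.25810 × 0.04224 = 0.0109, which is 6.06% − 4.97%.
- q = 0.06: 0.11345 × 0.50630 = 0.0574, which is the difference between 85.8% and 80.0% before rounding.

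Given exactly 2 SADE patients in 22, both are in the first 11 with probability C(11,2)/C(22,2) = 55/231 = 23.8%, at any common rate.

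**4. Alternative without a stage-1 limit.** The largest total that keeps 5% with 22 patients is 1: P(Bin(22, q) ≤ 1) = 0.0149 at q = 0.25 and 0.6163 at q = 0.06. Power falls to 61.6%.

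**5. Fewer than 22 evaluable.** Keep limits 1 and 2 but lose one patient from the second 11, so X2 ~ Bin(10, q). At q = 0.25: 0.04224 × 0.52559 + 0.15486 × 0.24403 = 0.02220 + 0.03779 = 0.0600. The two-stage rule itself then exceeds 5% unless the limit is recalculated under SAP 5.2.

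**The case against.** The best reply is that the SAP already settles the rule. SAP 7.2 is the operative analysis section and names Simon's rule. SAP 5.2 speaks of that rule's critical value. Table 2 states limits for both stages, not just a stopping instruction. SAP 2.10 terminates for futility, and a trial ended for futility does not conclude success. SAP 2.5 opens by calling the study two-stage, and in SAP 2.1 the termination rule stands immediately before the conclusion. SAP 5.4 still plans a pause after the first 11 patients reach 3 months. On this reading, 2 of 22 is only the second-stage limit.

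Much of this stands. A reader might infer that the trial's primary test runs at 6.06%. The documents do not support that: it is the error of the SAP 2.5 sentence taken alone, and the SAP read as a whole points to 4.97%. What does not stand is that the conflict can be ignored. Nothing in SAP 2.5 says which rule prevails, and SAP 8.2 records that the first two DSMB meetings came earlier than SAP 5.4 planned.

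A reader might also infer that the stage-1 check was skipped, or that the DSMB timing inflated the error. SAP 8.2 records no 3-month stage-1 check, but one may have taken place. The timing does not itself change the error, provided the stage-1 limit is applied to the claim.

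The addendum is limited evidence. It shows the total-only reading written down once with alpha at 0.05, but it amends Rev C. Whether Rev. G keeps that text is unknown, and it cannot fix the meaning of a later SAP.

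**Conclusion.** The point holds as a conflict within the SAP over one reachable outcome. The conclusion sentences in SAP 2.1 and 2.5 carry a 5% claim that the total-only rule does not meet (6.06%). The rule in SAP 7.2 meets it (4.97%, power 80.0%). The disputed outcome has probability 1.09% at a 25% SADE rate and 5.7% at 6%; every other outcome is decided alike. The addendum's amended 9.2 is wrong on alpha as written, since 2 or fewer in 22 with no stage-1 limit does not keep 5%.

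The figures assume 22 evaluable patients, independent outcomes and one common SADE rate in both halves.

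Correcting the text should not be presented as blind pre-specification. SAP 8.2 reports, in the past tense, an interim analysis after all subjects had completed the 6-month visit, so the 3-month safety data had already been collected. The correction aligns the text with a rule that SAP 7.2 already names. It is worth making because it concerns the only test in the trial and takes a few sentences.

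**What to change.** 1. In SAP 2.1 and 2.5, with a matching clause in 7.2, state that safety is concluded only if at most 1 of the first 11 patients and at most 2 of all 22 had an SADE within 3 months, whether or not the trial was actually stopped at stage 1. With 2 or more in the first 11, safety is not shown, whatever the total.
2. In the same place, state that the overall limit is recalculated under SAP 5.2 if fewer than 22 patients are evaluable.
3. Correct the alpha statement in protocol section 9.2 if the addendum's wording persists in Rev. G.
4. Record the change, before hard lock, as aligning the text with SAP 7.2, and note that 6-month data had already been analysed.

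The cost is a few sentences of text; no new patients, visits or analyses are needed. The downside is that power stays at the planned 80.0% rather than the 85.8% of the total-only rule, and that 2 SADE patients in the first 11 means safety is not shown even if the next 11 have none. Dropping the stage-1 limit and tightening the total to 1 of 22 would also keep 5%, but with only 61.6% power.

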7.6.3	Ophthalmic examinations	24
8.	Special Statistical/Analytical Issues	25
8.1	Interim Analysis	25
8.2	Changes in the Planned Analysis	26
A.	APPENDICES	28
	List of Tables	28
	List of Figures	30
	List of Listings	31

List of Abbreviations and Key Terms

α	Type I error
ADE	Adverse Device Effect
AE	Adverse Event
ASIC	Application specific integrated circuit
ATC	Anatomical Therapeutic Chemical Classification
β	Type II error
CIP	Clinical Investigation Plan
DSMB	Data Safety Monitoring Board
FAS	Full-analysis-set
GAT	Goldmann Applanation Tonometry
HLT	High level term
HLGT	High level group term
IO	Intraocular
IOL	Intraocular lens
IOP	Intraocular Pressure
ITT	Intention to treat
LLT	Lowest level term
N	Sample number
OCT	Ophthalmic Coherence Tomography
p0	Proportion of patients in stage 1 with positive outcome
p1	Proportion of patients overall with positive outcome
POAG	Primary open angle glaucoma
PT	Preferred term
SADE	Serious Adverse Device Effect
SAE	Serious Adverse Event
SAP	Statistical Analysis Plan
SES	Safety evaluation set
SOC	System organ class
V	Visit

1. Introduction

This Statistical Analysis Plan (SAP) contains a more technical and detailed elaboration of the principal features of the statistical analyses described in the Clinical Investigation Plan Rev. G, date 05th January 2016, and includes planned detailed procedures for executing the statistical analysis of the primary and secondary variables and other data. The SAP is finalised and signed prior to hard lock of the database.

2. Study Design and Objectives

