7.3 Evaluation of Primary Performance Variables

The primary performance objective is the assessment of the agreement between measurements made using GAT and the ARGOS-IO system from V05 (day 30) through V09 (day 180). If multiple ARGOS-IO system measurements have been made at time points for which paired GAT/ARGOS-IO system measurements are to be compared, the mean of the replicate ARGOS-IO system measurements will be used for agreement evaluation. The agreement evaluation is based on the assumption, that the measurements are constant over the measurement period.

The Bland-Altman method, which compares the mean of paired measurements to their difference will be used to determine the upper and lower limits of agreement expected to contain 95% of the IOP value pairs obtained with the ARGOS-IO system and GAT. The two-sided 95% confidence intervals for each of these limits will be calculated using the Mover method (Zou, 2011) to account for repeated measurements. IOP values will be displayed as Bland-Altman plots of individual measurement pairs by measurement technique for each individual participant as well as mean plots over time (per visit and overall). This analysis is based on the FAS and is repeated for each subgroup as described in section 4.2.

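### SAP 2.5 prints the primary safety hypotheses at 0.25 instead of 0.75 on the SADE-free scale, and SAP 2.5 and 7.2 offer a 6% conclusion that no result in 22 patients can reach

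*SAP*

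**What the plan says.** SAP 2.5 puts the hypothesis in words: "The specific hypothesis to be tested in this single arm two-stage design study is that the SADE rate is lower than 25" percent. It then sets the notation, "let p be the true proportion of subjects with no SADEs", and prints H0 as p at or below p0 = 0.25 and H1 as p above p1 = 0.25.

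SAP 2.9 (text and Table 2) and SAP 7.2 use p0 = 0.75 and p1 = 0.94, both SADE-free proportions. The decision rule is to stop if more than 1 of the first 11 patients has a SADE, and to conclude a rate below 25% if at most 2 of 22 do.

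On the supporting interval, SAP 2.5 says: "This will be illustrated by the 95% confidence interval for the SADE rate", using the Koyama-Chen method. It adds that if the "confidence interval does not include any value lower than 0.94, it can be concluded that the SADE rate is at most 6" percent. SAP 7.2 repeats this criterion. Neither section converts the interval to the SADE-free scale or gives its sidedness. SAP 7.3, by contrast, is explicit for the agreement limits: "The two-sided 95% confidence intervals for each of these limits will be calculated using the Mover method".

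The SAP implements "Clinical Investigation Plan Rev. G, date 05th January 2016", which was not supplied. Section 7.2 of the supplied CIP Rev C gives the tested hypothesis as a SADE rate of at most 6% and makes the description of agreement depend on its being proven.

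**The concern.** SAP 5.3 says that only the primary safety variable is tested, so this is the trial's single confirmatory hypothesis. As printed, the null says that at least 75% of patients have a SADE. That contradicts the sentence just before it and the design parameters.

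The 6% sentence has two faults. It compares an interval for one proportion with a threshold for its complement. It also promises a conclusion that looks out of reach with 22 patients, whatever the data show.

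Finally, a one-sided 5% test is to be illustrated by an interval of unstated sidedness. If that interval is two-sided 95%, the report could conclude a rate below 25% beside an interval that contains 25%.

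**Working it through.** **Inputs** (SAP 2.5, 2.9, 2.10 and 7.2): n1 = 11 and N = 22; continue if at least 10 of 11 are SADE-free; pass if at least 20 of 22 are; p0 = 0.75, p1 = 0.94, type I error 5%, power 80%. Below, p is the SADE-free proportion.

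**1. Reproduce the design.** With X1 and X2 the SADE-free counts in the two stages of 11:

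P(pass) = P(X1 = 11)·P(X2 ≥ 9) + P(X1 = 10)·P(X2 ≥ 10)

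- p = 0.75: 0.04224 × 0.4552 + 0.15486 × 0.1971 = 0.0497
- p = 0.94: 0.5063 × 0.9752 + 0.3555 × 0.8618 = 0.8001
- Expected sample size at 0.75: 11 + 11 × 0.1971 = 13.17, which matches the 13.2 in CIP Rev C 9.2.

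The stated 5% and 80% therefore hold for p0 = 0.75 and p1 = 0.94.

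**2. Try the printed null.** At p = 0.25 the same rule passes with probability 9.4e-11. The rule was not built on 0.25, which is the SADE-rate complement of 0.75.

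**3. Interval limits.** The lower limit L of the SADE-free proportion solves P_L(X1 ≥ 10 and X1 + X2 ≥ x) = 0.025 (two-sided 95%) or 0.05 (one-sided 95%). The SADE-rate upper limit is 1 − L.

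| SADEs in 22 | L, two-sided | SADE upper limit | L, one-sided | SADE upper limit |
|---|---|---|---|---|
| 0 | 0.8456 | 15.4% | 0.8727 | 12.7% |
| 1 | 0.7716 | 22.8% | 0.8019 | 19.8% |
| 2 | 0.7177 | 28.2% | 0.7502 | 24.98% |

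Clopper-Pearson limits are identical at 0 and 1 SADE, because the stage 1 stop cannot exclude any path to those totals. At 2 SADEs they are slightly lower (0.7084 and 0.7405).

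**4. Apply the 0.94 criterion.**

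- On the SADE-free scale, L must be at least 0.94. The best possible L is 0.846 or 0.873, so the criterion always fails.
- On the SADE-rate scale as written, even 22 of 22 SADEs would give 0.025^(1/22) = 0.846 or 0.05^(1/22) = 0.873. The stage 1 rule prevents that outcome. For 11 of 11 at stage 1 the two-sided limit is 0.025^(1/11) = 0.715. Meeting the criterion on this scale would in any case mean a SADE rate of at least 94%.
- If the true SADE rate is exactly 6%, a clean 0/22 still occurs with probability 0.94^22 = 0.256, so 0/22 cannot exclude rates above 6%.
- Patients needed with zero events: ln(0.05)/ln(0.94) = 48.4, so 49 (one-sided); ln(0.025)/ln(0.94) = 59.6, so 60 (two-sided).

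**5. Agreement between interval and test.** Among passing results, only the two-sided interval at exactly 2 SADEs contains 25%. At a true SADE rate of 6%, P(pass with exactly 2) = 0.8001 − 0.6163 = 0.1838, where 0.6163 is the probability of at most 1 SADE in 22. That is 0.1838/0.8001 = 23.0% of passing trials.

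**The case against.** The strongest reply is that little depends on this. The hypothesis in words, the count rule, Table 2 and SAP 7.2 all show that 0.75 is meant, and a programmer following 7.2 would use it. A SADE-rate interval and a SADE-free interval are exact complements, so 0.94 can be read charitably. A rule that never fires produces no false claim. All of this is true and limits the seriousness. It does not make the printed null right, and the charitable reading does not make the 6% rule attainable.

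On sidedness, an unqualified 95% interval is usually taken as two-sided, and reporting one beside a one-sided test is common. The decision rests on the count, and the interval only illustrates it. Even so, SAP 2.5 gives the interval the job of illustrating the conclusion, and at 2 SADEs a two-sided one does not.

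The formula was read from PDF by a program. The same misreading twice, landing on the complement of 0.75, is unlikely, but a look at the original page will settle it. Finally, SAP 2.5 already uses below 25% as the tested hypothesis and SAP 7.3 analyses agreement without any condition, so Rev G may already have dropped the Rev C wording. Any CIP edit is therefore conditional.

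**Conclusion.** The concern holds and should be fixed before the SAP is used for the final report. The printed null of 0.25 is wrong for p as defined; 0.75 is the value that gives the stated 5% and 80%. H1 also labels 0.25 as p1, which is 0.94 elsewhere. The 6% conclusion is void: the smallest attainable SADE-rate upper limit is 12.7% (one-sided) or 15.4% (two-sided). Under a two-sided reading, a pass with 2 SADEs would be reported with an interval up to 28.2%.

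The pass rule, its error rates and the sample size do not change.

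Two assumptions apply. The limits come from inverting the two-stage tail probability for the planned 11 + 11 patients, taken as the Koyama-Chen form because the cited paper was not supplied. They would shift if drop-outs led to the recalculated critical value in SAP 5.2.

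**What to change.** - **SAP 2.5:** write H0: p ≤ 0.75 against H1: p > 0.75, with p the SADE-free proportion. Keep p1 = 0.94 only as the alternative at which power was calculated.
- **SAP 2.5 and 7.2:** delete the sentence linking 0.94 to a rate of at most 6%. Keep 6% only as the expected rate. State that passing supports a SADE rate below 25%, with the interval reported as observed; it will be tighter at 0 or 1 SADE.
- **SAP 2.5 and 7.2:** state the sidedness of the Koyama-Chen interval. Report the one-sided 95% upper bound beside, or in place of, the two-sided 95% interval so that it agrees with the one-sided 5% test.
- **CIP:** only if the current revision keeps the Rev C text of section 7.2, replace at most 6% with below 25% and remove the condition on describing agreement.

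The cost is a few lines of wording and one extra reported bound. Data, sample size and decision rule stay as they are.
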